8.2. Secondary Efficacy Analyses

This section describes the planned analyses for the secondary efficacy outcome measures. Where applicable, refer to Section 6.1 for SAS pseudocode. Analyses of mortality will be described in Section 9.4.

Analyses of the key secondary outcome measure will be explored in the specified subgroups described in Section 6.4. Analyses of the other secondary outcome measures will be performed by treatment arm only and repeated for specified subgroups described in Section 6.4 and Section 6.7 via stratified analyses. As with the analyses described in Section 8.1.2, tabular summaries will follow the structure of the main tabular summaries planned for each outcome with the modification that stratified estimates will be provided in separate rows. Forest plots will display confidence intervals of outcomes/estimates across subgroups, where applicable.

All secondary efficacy analyses will be performed in the ITT population. Treated analyses will be explored to investigate consistency of results compared to the ITT analyses.

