4.2.3. Method of Assigning Subjects to Treatment Groups (Randomization)

Enrollment and randomization of subjects is done online using the enrollment module of Advantage eClinical[®].

Eligible subjects will be randomized and assigned in a 1:1 ratio to either remdesivir or placebo, with stratification by site and disease severity (Mild/Moderate disease or Severe disease). The randomization is based on a variable blocked scheme to provide an approximately balanced allocation to the treatment groups during the study. If arms are added or removed later in the study, randomization will continue in an equal allocation manner.

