8.2.1. Ordinal Scale Outcomes (Key Secondary Outcome Measure)

For the analysis of the key secondary outcome measure, the distribution of the 8-point ordinal clinical status scale with 8 categories at Study Visit Day 15 (not necessarily actual study day 15), the outcome will be analyzed using a proportional odds model with treatment arm and disease severity as covariates. The treatment odds ratio estimated from the model will be presented along

with the p-value (Table 24). Predicted individual probabilities of scale levels by treatment arm and disease severity will be summarized graphically (Figure 10).

As noted in Section 3.3, sensitivity analyses will be performed to account for subjects who are unblinded as well as placebo subjects who are unblinded and crossover treated with remdesivir. These analyses will be performed in the ITT population.

Multiple supplemental analysis of this key secondary outcome will be performed. Time to improvement by at least one category in the clinical status 8-point scale (see Section 3.3). The log rank test will be performed using a Cox proportional hazards model to test whether the curves differ between treatment arms. The median time to event and CI in each treatment group will be summarized along with the treatment hazard ratio estimate and log rank p-value (Table 26). Differences in time-to-event endpoints by treatment arm will be summarized with Kaplan-Meier curves (Figure 11). Number at risk, hazard ratio and log rank p-values will be presented on the figures. The analyses (and tabular and graphical summaries) will be repeated using the outcome of time to improvement in two categories of the ordinal scale defined in Section 3.3. Both time to improvement (one and two categories) analyses will be repeated using the censoring plan described in Section 3.3 for subjects who are retreated with remdesivir (Table 28). In addition, a subgroup analysis time to improvement among subjects enrolled with a clinical score of 7 will be performed using the retreatment censoring plan (Table 29).

The above analyses will be repeated with the following modification to the ordinal scale described in Section 4.3 (Table 29).

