8.2.2. NEWS

The median time to discharge or to a NEWS of ≤ 2 and CI will be summarized by treatment group (Table 36). The hazard ratio and log rank p-values will be provided with the summaries. Differences in time-to-event endpoints by treatment arm will be summarized with Kaplan-Meier curves. Number at risk, hazard ratio and log rank p-values will be included on the figures (Figure 15).

The mean, standard deviation (SD), median, minimum, and maximum NEWS at Baseline and Study Visit (not necessarily actual) Days 3, 5, 8, 11, 15 and 29 will be presented by treatment arm as well as change from baseline at each post-Day 1 visit (Table 39). A figure with mean and SD over time will also be presented by treatment arm (Figure 16).

Subject listings of NEWS responses (overall and individual components) by day will be generated (Listing 6).

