9.4. Deaths, Serious Adverse Events and other Significant Adverse Events

A listing of death and other serious adverse events will be presented, including Subject ID, treatment group, Adverse Event Description, Associated Dose Number, Number of Days Post Dose (Duration), Number of Days Post Dose the Event Became Serious, Reason Reported as an SAE, Severity, Relationship to Treatment, Alternate Etiology if not Related, Action Taken with

Study Treatment, Subject Discontinuation, Outcome, MedDRA SOC, and MedDRA PT (Listing 12 and Listing 13).

The number of subjects who die by Day 15 and Day 29 will be presented by treatment arm. The 14- and 28-day crude mortality rate, which will use the number of subjects in the treatment group and analysis population as the denominator, will be presented (Table 59). The analysis will be repeated censoring placebo subjects who were retreated with remdesivir at the time of retreatment.

Mortality through Day 15 and 29 will also be analyzed as a time to event endpoint (see Section 3.3). A table will present median time to event along with 95% confidence intervals overall for each treatment arm along with the hazard ratio estimate and log rank p-values (Table 61). Differences in time-to-event endpoints by treatment will be summarized with Kaplan-Meier curves (Figure 23). Analyses of mortality will be performed in the ITT and the Treated analysis populations and will be performed on both the early and the full analysis sets.

The ITT tabular summaries will be repeated censoring placebo subjects who were retreated with remdesivir at the time of retreatment. Similarly, the summaries will be repeated censoring subjects who were unblinded at the time of unblinding.

Rates of Grade 3 and 4 AE occurrence will be compared between treatment arms using Barnard's exact test and presented (Table 63). Rates of SAE occurrence will also be compared between treatment arms using Barnard's exact test and presented. Further, the composite endpoint of the occurrence of death, SAE, or Grade 3 or 4 AE described in Section 3.3 will be analyzed as a time to event outcome. A table will present median time to event along with 95% confidence intervals overall for each treatment arm along with the hazard ratio estimate and log rank p-values (Table 64). Differences in time-to-event endpoints by treatment will be summarized with Kaplan-Meier curves (Figure 24).

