		Mild-Moderate (N=X)		Severe (N=X)		Mild-Moderate (N=X)		Severe (N=X)		Mild-Moderate (N=X)		Severe (N=X)	
		# of Subj.	# of Dev.	# of Subj.	# of Dev.	# of Subj.	# of Dev.	# of Subj.	# of Dev.	# of Subj.	# of Dev.	# of Subj.	# of Dev.
	Required procedure done incorrectly	x	x	x	x	x	x	x	x	x	x	x	x
	Study product temperature excursion	x	x	x	x	x	x	x	x	x	x	x	x
	Specimen temperature excursion	x	x	x	x	x	x	x	x	x	x	x	x
	Other	x	x	x	x	x	x	x	x	x	x	x	x
Treatment administration	Any type	x	x	x	x	x	x	x	x	x	x	x	x
	Required procedure done incorrectly	x	x	x	x	x	x	x	x	x	x	x	x
	Study product temperature excursion	x	x	x	x	x	x	x	x	x	x	x	x
	Other	x	x	x	x	x	x	x	x	x	x	x	x
Blinding policy/procedure	Any type	x	x	x	x	x	x	x	x	x	x	x	x
	Treatment unblinded	x	x	x	x	x	x	x	x	x	x	x	x
	Other	x	x	x	x	x	x	x	x	x	x	x	x

N = number of subjects enrolled

Tables with similar format:

Table 13: Distribution of Protocol Deviations by Category, Type, and Site

Table 14: Time to Recovery by Treatment Group and Disease Severity

Analysis Population	Treatment Group	Disease Severity	n	Median Time to Recovery		HR		P-value
				Estimate	95% CI	Estimate	95% CI	
ITT Population	Remdesivir (N=X)	Mild/Moderate	x	x.x	x.x, x.x	x.x	x.x, x.x	0.xxx
	Placebo (N=X)		x	x.x	x.x, x.x			
	Remdesivir (N=X)	Severe	x	x.x	x.x, x.x	x.x	x.x, x.x	
	Placebo (N=X)		x	x.x	x.x, x.x			
	Remdesivir (N=X)	Any Severity	x	x.x	x.x, x.x	x.x	x.x, x.x	
	Placebo (N=X)		x	x.x	x.x, x.x			

Repeat for the Treated Population.

N= Number of subjects in the specified treatment group, disease severity, and analysis population.

n = Number of recovered subjects.

HR for the ‘Any Severity’ group is the hazard ratio from the stratified Cox Model.

P-value calculated using the stratified log-rank test

Tables with similar format:

Table 15: Time to Recovery by Treatment Group and Disease Severity: Fine-Gray and Interaction Modeling

Table 16: Time to Recovery by Treatment Group within Subgroups – ITT Population

Table 17: Time to Recovery by Treatment Group within Subgroups – Treated Population

Table 18: Time to Recovery by Treatment Group and Disease Severity: Readmittance Sensitivity Analysis – ITT Population

Table 19: Time to Recovery by Treatment Group and Disease Severity: Concomitant Medication Sensitivity Analysis – ITT Population

Table 20: Time to Recovery by Treatment Group and Disease Severity: Unblinding and Crossover Treatment Sensitivity Analysis – ITT Population

Programming Notes for Table 15:

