Treatment Group	Grouping Variable	Subgroup	Recovered		Did Not Recover		Deaths		Not Recovered or Died	
			n	%	n	%	n	%	n	%
Remdesivir (N=X)	Disease Severity	Mild/Moderate	x	x	x	x	x	x	x	x
Placebo (N=X)			x	x	x	x	x	x	x	x
Remdesivir (N=X)		Severe	x	x	x	x	x	x	x	x
Placebo (N=X)			x	x	x	x	x	x	x	x
Remdesivir (N=X)		Any Severity	x	x	x	x	x	x	x	x
Placebo (N=X)			x	x	x	x	x	x	x	x
Continue for duration of symptoms categories in Section 6.4										
N= Number of subjects in the ITT Population.										

Implementation Note: For the symptom categorizations, the Grouping Variable column will display “Duration of Symptoms prior to enrollment”.

Table 23: Odds Ratio for Inferior Clinical Status Score at Study Visit Day 15 by Treatment Using a Proportional Odds Model – ITT Population

Covariate	Treatment Group	Odds Ratio		P-value
		Estimate	95% CI	
Disease Severity	Remdesivir (N=X)	x.x	x.x, x.x	0.xxx
	Placebo (N=X)			
[Continue for each Section 6.4 subgroups]	Remdesivir (N=X)	x.x	x.x, x.x	0.xxx
	Placebo (N=X)			
The specified covariates were included individually in separate models.				

Table with similar format:

Table 24: Odds Ratio for Inferior Clinical Status Score at Study Visit Day 15 by Treatment Using a Proportional Odds Model – Treated Population

Table 25: Odds Ratio for Inferior Clinical Status Score at Study Visit Day 15 by Treatment Using a Proportional Odds Model – Unblinding and Crossover Treatment Sensitivity Analysis – ITT Population

Table 26: Time to Improvement on the 8-Point Ordinal Scale by Treatment Group

Analysis Population	Treatment Group	n	Median Time		HR		P-value
			Estimate	95% CI	Estimate	95% CI	
Improvement by at least One Category							
ITT Population	Remdesivir (N=X)	x	x.x	x.x, x.x	x.x	x.x, x.x	x.xxx
	Placebo (N=X)	x	x.x	x.x, x.x			
Treated Population	Remdesivir (N=X)	x	x.x	x.x, x.x	x.x	x.x, x.x	x.xxx
	Placebo (N=X)	x	x.x	x.x, x.x			
Improvement by at least Two Categories							
ITT Population	Remdesivir (N=X)	x	x.x	x.x, x.x	x.x	x.x, x.x	x.xxx
	Placebo (N=X)	x	x.x	x.x, x.x			
Treated Population	Remdesivir (N=X)	x	x.x	x.x, x.x	x.x	x.x, x.x	x.xxx
	Placebo (N=X)	x	x.x	x.x, x.x			

N = Number of subjects in the specified treatment group and analysis population.
n = Number of subjects with improvement.
HR is the hazard ratio from the Cox Model
P-value calculated using the Log-rank test

Tables with similar format:

Table 27: Time to Improvement on the 8-Point Ordinal Scale by Treatment Group: Remdesivir Retreatment Sensitivity Analysis

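### The log-rank and Cox analyses of discharge or NEWS ≤2, of improvement and apparently of death read as unstratified, although randomization and the primary test are stratified by severity

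*SAP*

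**What the plan says.** SAP Section 4.2.3 allocates subjects 1:1 "with stratification by site and disease severity (Mild/Moderate disease or Severe disease"). SAP Section 8.1.1 stratifies the primary log-rank test by severity. The Table 14 footnotes say the overall HR comes from the stratified Cox model and, for the test, "P-value calculated using the stratified log-rank test". The key secondary proportional odds model (Section 8.2.1) has severity as a covariate.

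For the other secondary outcomes, Section 8.2 says "Analyses of the other secondary outcome measures will be performed by treatment arm only". It then plans subgroup repeats in which "stratified estimates will be provided in separate rows".

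- **Discharge or NEWS ≤2** (Section 8.2.2): "The hazard ratio and log rank p-values will be provided with the summaries". No strata are mentioned. The Table 36 footnote reads "P-value calculated using the Log-rank test".
- **Time to improvement** (Section 8.2.1): "The log rank test will be performed using a Cox proportional hazards model to test whether the curves differ between treatment arms". The Table 26 footnote matches that of Table 36.
- **Death** (Section 9.4, to which Section 8.2 defers mortality): median times are given "overall for each treatment arm along with the hazard ratio estimate and log rank p-values (Table 61"). No strata are mentioned, and the Table 61 footnote is again plain.

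Section 6.1 gives stratified code for the final time-to-event analyses and explains how to drop the strata line for unstratified ones. It does not say which endpoints get which form.

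**The concern.** A factor used to constrain randomization would normally be carried into the analysis. Here that is done for the primary and key secondary endpoints and then, as written, stops. If severity predicts the outcome, an unstratified log-rank test after stratified randomization gives up some power, and the unstratified HR drifts toward 1. The recovery HR and the HRs for NEWS, improvement and death would then be estimated on different bases within one report.

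There is also a specification gap. Because Section 6.1 assigns neither form of the code to an endpoint, two programmers could report different mortality HRs and p-values, each in keeping with the SAP.

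**Working it through.** **1. What each table specifies.** The Table 14 footnotes use the word stratified for both the HR and the p-value. The footnotes of Tables 26, 36 and 61 use it for neither. For NEWS, Section 8.2 and the footnote agree. For improvement, the footnote is plain, but whether the Section 8.2 sentence applies is arguable: Section 3.1 lists improvement among the other secondary objectives, while Section 8.2.1 places it under the key secondary outcome. For death, the Section 8.2 sentence does not apply, so only silence and the footnote remain.

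**2. Whether the subgroup repeats supply the missing test.** Section 6.4 lists randomized stratum and baseline category as subgroups for all secondary outcomes. Separate rows give one estimate per stratum. They do not give a pooled stratified HR or a pooled test.

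**3. The plan's own figure.** For the primary endpoint, 4(1.96 + 1.036)² / (ln 1.35)² = 398.8 events, against 400 stated. Power at 400 events is 85.1%. This figure stands and is not at issue. The documents state no power for improvement, NEWS or death.

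**4. Size of the loss.** The documents give no case mix or event rates by baseline category, so these are assumed.

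- Mix A: 15/40/20/25% in categories 4/5/6/7. With 60% of category 4 in the mild/moderate stratum, that stratum holds 0.15 × 0.60 = 9%.
- Mix B: 30/35/15/20%. With 80% of category 4 in the mild/moderate stratum, it holds 0.30 × 0.80 = 24%.
- N = 572, 1:1 within severity stratum, exponential times within category rounded up to whole days, subjects without the event at risk to day 28.
- Log-rank Z as in Section 8.1.1, with one stratum or two, two-sided 5%. 20,000 trials per cell (Monte Carlo error about 0.0035).

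| Endpoint, true HR | 28-day rates in categories 4/5/6/7 (%) | Mix | Power, unstratified | Power, by severity | Gain (points) |
|---|---|---|---|---|---|
| NEWS ≤2 or discharge, 1.25 | 80/79/77/75 | A | 0.67 | 0.67 | 0 |
| | 92/85/68/50 | A | 0.54 | 0.56 | 2 |
| | 92/85/68/50 | B | 0.57 | 0.61 | 4 |
| | 95/90/60/35 | A | 0.42 | 0.45 | 3 |
| | 95/90/60/35 | B | 0.43 | 0.51 | 8 |
| One-category improvement, 1.25 | 85/84/82/80 | A | 0.70 | 0.70 | 0 |
| | 92/88/78/62 | A | 0.61 | 0.62 | 1 |
| | 92/88/78/62 | B | 0.62 | 0.64 | 2 |
| Death, 0.6 | 10/11/12/13 | A | 0.45 | 0.45 | 0 |
| | 4/8/18/24 | A | 0.49 | 0.49 | 0 |
| | 4/8/18/24 | B | 0.44 | 0.44 | 0 |
| | 2/5/20/35 | A | 0.52 | 0.52 | 0 |
| | 2/5/20/35 | B | 0.43 | 0.45 | 2 |

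A separate simulation of six mix and rate settings (4,000 trials each) agreed within about 0.02. At N = 800, the NEWS 92/85/68/50 cell for mix A is 0.69 against 0.71, and the death 2/5/20/35 cell for mix A is 0.66 against 0.66.

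**5. Dilution and validity.** In the NEWS 92/85/68/50 cell, mix A, true HR 1.25, the mean estimated HR is 1.212 unstratified and 1.217 stratified by severity. The type I error of the unstratified test was 0.041 to 0.053.

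**6. Recovery tables.** Section 8.1.2 repeats the primary analysis with each Section 6.4 factor in place of severity and promises the same tables. The programming note for Tables 16 and 17 then drops the pooled rows, where Table 14 carries the stratified HR. The two instructions need reconciling.

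**The case against.** The strongest reply is that Section 6.1 makes stratified code the default for final time-to-event analyses, and that Section 6.3.1 classifies subjects by randomized severity for the main secondary efficacy analyses too. On that reading the footnotes are merely brief. This stands in part. It is why death can only be called apparently unstratified, and why for death the firm defect is ambiguity. It does not rescue NEWS, where Section 8.2 and the footnote point the same way. Section 6.3.1 fixes which severity label is used, not whether the test uses it.

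A second reply is that the subgroup rows can be pooled by hand. For NEWS this works for the estimate: in a 600-trial check, inverse-variance pooling of four category HRs gave 1.239 against 1.240 from a stratified Cox model. It still supplies no prespecified test. It works poorly for sparse death data (SD of the log HR difference 0.055), and no subgroup shell for death is listed.

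A reader might infer a much larger loss. Supplemental oxygen alone scores 2 on NEWS, two-category improvement means 7 to 5 for one subject and discharge for another, and stratifying by four baseline categories raises simulated power more. Those arguments mainly concern baseline category, which was not a randomization factor, so they do not measure this departure from the design. Likewise, borrowing the primary endpoint's 400 events and ratio of 1.35 gives an unstratified power as low as 68%. That needs an assumed fivefold severity effect with 70% severe, and it does not describe these endpoints.

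Site was also a randomization factor and is not in the primary strata, so agreement with the randomization would be partial in any case.

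**Conclusion.** The point holds as a modest one. The main analysis of discharge or NEWS ≤2 is unstratified as written. Improvement reads the same way with some doubt about which sentence governs it, and death only apparently. The cost is inconsistency with the design and, if severity is prognostic, about 0 to 8 points of power for NEWS, 0 to 2 for improvement and 0 to 2 for death, with slight dilution of the HR. These ranges rest entirely on assumed mixes, rates and effects. With no prognostic spread nothing is lost.

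The documents do not support reading this as an invalid test or an inflated type I error. Nor do they support reading it as a flaw in the primary analysis, whose test, boundaries and 400-recovery target are unaffected. A reader might also infer that the pooled category-stratified recovery HR disappears altogether. Section 8.1.2 has Figure 6 showing an overall HR, so it may survive there; only the table row is dropped.

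**What to change.** - **Section 6.1:** state that the main log-rank and Cox analyses of time to improvement (one and two categories), discharge or NEWS ≤2, and death are stratified by randomized severity, as for the primary endpoint. Name the composite safety endpoint of Table 64 as well, since its footnote has the same wording.
- **Footnotes:** change Tables 26, 36 and 61 to match, with Tables 27, 62 and 64, which share their format or footnote.
- **Headline:** name the severity-stratified result as the main one, keep the unstratified result as a sensitivity analysis, and label the change as made after the interim results were disclosed (Section 2.1).
- **Optional:** for improvement and NEWS, add a pooled HR stratified by baseline category (4; 5; 6; 7), with a 95% CI and no p-value, as a supportive estimate. No rule for collapsing strata is needed.
- **Recovery:** reconcile Section 8.1.2 with the note for Tables 16 and 17 by keeping the pooled row for baseline category, without a p-value. The primary test and boundaries stay as they are.

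The cost is a sentence, a strata line, a few footnotes and one table row. No new data are needed. The real downside is that the choice is made after results were public. Labelling discloses this but does not remove it.

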8.2.1. Ordinal Scale Outcomes (Key Secondary Outcome Measure)

For the analysis of the key secondary outcome measure, the distribution of the 8-point ordinal clinical status scale with 8 categories at Study Visit Day 15 (not necessarily actual study day 15), the outcome will be analyzed using a proportional odds model with treatment arm and disease severity as covariates. The treatment odds ratio estimated from the model will be presented along

with the p-value (Table 24). Predicted individual probabilities of scale levels by treatment arm and disease severity will be summarized graphically (Figure 10).

As noted in Section 3.3, sensitivity analyses will be performed to account for subjects who are unblinded as well as placebo subjects who are unblinded and crossover treated with remdesivir. These analyses will be performed in the ITT population.

Multiple supplemental analysis of this key secondary outcome will be performed. Time to improvement by at least one category in the clinical status 8-point scale (see Section 3.3). The log rank test will be performed using a Cox proportional hazards model to test whether the curves differ between treatment arms. The median time to event and CI in each treatment group will be summarized along with the treatment hazard ratio estimate and log rank p-value (Table 26). Differences in time-to-event endpoints by treatment arm will be summarized with Kaplan-Meier curves (Figure 11). Number at risk, hazard ratio and log rank p-values will be presented on the figures. The analyses (and tabular and graphical summaries) will be repeated using the outcome of time to improvement in two categories of the ordinal scale defined in Section 3.3. Both time to improvement (one and two categories) analyses will be repeated using the censoring plan described in Section 3.3 for subjects who are retreated with remdesivir (Table 28). In addition, a subgroup analysis time to improvement among subjects enrolled with a clinical score of 7 will be performed using the retreatment censoring plan (Table 29).

The above analyses will be repeated with the following modification to the ordinal scale described in Section 4.3 (Table 29).

The number and proportion of subjects along with 95% confidence intervals by category of clinical status will be presented by treatment arm at Study Visit (not necessarily actual) Days 1, 3, 5, 8, 11, 15 and 29 (Table 34). A figure will present stacked bar charts by day with side by side bars for each treatment arm (Figure 13). Histograms will be generated to display the ordinal scale value distributions over time in each treatment group (Figure 14).

